6.7 EVERY 6 MONTHS THEREAFTER AND UNSCHEDULED VISITS

Visits occurring after the 12 month visit should occur every 6 months until completion of the study (18 months \pm 60 days, 24 months \pm 60 days etc. after the implant). An unscheduled follow-up is defined as a visit that occurs between two scheduled study visits where the subject is examined for either a physician or investigator requested follow-up or for an adverse event. The following assessments will be performed at these visits:

- Adverse event assessment (SAE, ADE, SADE that occurred since the last study visit)
- Heart failure medication review
- Anticoagulant/antiplatelet medication review

- PA pressure measurements may be obtained at the investigator's discretion
- Reporting of any HF hospitalization that have occurred since the subject was last seen

The data collected must be documented by completing the appropriate CRF.

Between study visits, the subject will be followed remotely using the CardioMEMS HF System for the collection of pulmonary artery pressure measurements. Subjects will be instructed to take daily readings and trend data will be reviewed by a healthcare professional experienced in the management of heart failure at least once every 7 days. Medication or treatment regimen changes as a result of PAP data review will be reported.

All telephone contacts between site staff and the subject should be documented using the Subject Contact Log (refer to Appendix K) and the following information should be captured:

- Date of contact
- Reason for contact
- Ability to reach the subject (Call success)
- Name and role of person contacting the patient
- Call outcome (Instructions given) with the reason medication was changed, if applicable (PAP guided or signs and symptoms guided)
- Other action required

Guidelines for Standardized Post-discharge Heart Failure Care

The subject should be contacted by telephone weekly during the first month and two weekly (for NYHA class III/IV subjects) and four weekly (for NYHA class I/II subjects) weekly thereafter depending on HF symptoms severity to ensure standardized HF monitoring and education. A standardized 14-item questionnaire (structured interview) addressing general health, indicators of worsening HF, state of mood, well-being, and medication should be used to drive and to document the interaction between the subject and site staff (refer to Appendix L). A self-assessment booklet and a booklet containing information on HF-associated symptoms should be provided to the subject together with appropriate training on the content of both documents.

If the subject is contacted off-schedule to perform PAP guided medication changes, the subject does not need to be contacted again per the recommended standardized schedule during that time.

6.8 DESCRIPTION OF ACTIVITIES PERFORMED BY SPONSOR REPRESENTATIVES

Trained sponsor personnel may perform certain activities to ensure compliance to the clinical investigation plan and may provide technical expertise.

Sponsor personnel will not perform the informed consent process, practice medicine, provide medical diagnosis or treatment to subjects, discuss a subject's condition or treatment with a subject without the approval and presence of a health care practitioner, or independently collect clinical investigation data.

6.9 SUBJECT STUDY COMPLETION

Upon completion of the study, the subject's participation will be considered completed. When the subject's participation in the clinical study has been completed the subject will return to medical care as per physician's recommendation.

6.10 ANY KNOWN OR FORSEEABLE FACTORS THAT MAY COMPROMISE THE OUTCOME OF THE CLINICAL STUDY OR THE INTERPRETATION OF THE

Template: 86357 Rev. A

Page 28 of 65

Clinical Investigational Plan Template

RESULTS

All foreseeable factors that may compromise the outcome have been taken into account by clinical study design and well defined subject selection criteria.

Subject recruitment and retention will be monitored throughout the study and include (but are not limited to) the following activities: evaluation of the site and investigators, training of site personnel, and developing site support materials.

6.11 DESCRIPTION OF THE METHODS THAT WILL BE USED TO ADDRESS POTENTIALLY CONFOUNDING FACTORS IN THE CLINICAL STUDY DESIGN

This is a single arm study so there are no known confounding factors to be addressed for the primary safety endpoints and the primary clinical performance endpoint. The study design of using subjects serving as their own controls and within-subject comparisons of outcomes during 12 months following implant in the study and outcomes during 12 months prior to implant using frailty model accounts for unmeasured confounding factors for the secondary endpoint.

6.12 CRITERIA AND PROCEDURES FOR SUBJECT WITHDRAWAL OR DISCONTINUATION

Subjects must be informed about their right to withdraw from the study at any time and for any reason without sanction, penalty or loss of benefits to which the subject is otherwise entitled and withdrawal from the study will not jeopardize their future medical care or relationship with the investigator. Subjects will be asked to specify the reason for the termination, but have the right not to answer.

The investigator may decide to withdraw a subject from the study at any time with reasonable rationale. The subject's future care will not be influenced by a decision, voluntary or otherwise, to withdraw from the study. All reasonable efforts should be made to retain the subject in the clinical study until completion of the study.

Reasons for subject's withdrawal include, but are not limited to:

- Subject refuses to continue participating in the study
- Subject does not meet the inclusion/exclusion criteria and does not require additional follow-up for safety reasons.
- Subject is deceased (cause must be documented)
- Subject's non-compliance
- Subject's participation is terminated by the PI or investigator, although the subject consented, since participation is no longer medically appropriate
- Subject is lost to follow up: subject does not adhere to the scheduled follow up visits but has not
 explicitly requested to be withdrawn from the clinical study (this does not apply to missed visits).
 Site personnel should at all times make all reasonable efforts to locate and communicate with the
 subject in order to achieve subject compliance to the scheduled follow up visits:
 - 1. A subject will be considered 'Lost to Follow Up' after a minimum of 2 phone calls of a physician or delegate at the investigational site to the subject or contact. These 2 phone calls need to be documented in the subject's hospital records.
 - 2. If these attempts are unsuccessful, a letter should be sent to the subject's last known address or general practitioner (GP) and a copy of this letter should be maintained in the subject's hospital records.

Template: 86357 Rev. A

Page 29 of 65

Clinical Investigational Plan Template

Note: If a subject misses the 6-month visit, this will be considered as a missed visit. The subject may therefore still return for the 12-month visit and will not be excluded from the study.

If a subject withdraws from the clinical study, the site will record the subject's reasons for withdrawal on a withdrawal CRF.

When subject withdrawal from the clinical study is due to an adverse event, the subject will be followed until resolution of that adverse event or determination that the subject's condition is stable. The status of the subject's condition should be documented at the time of withdrawal.

Prior to withdrawal, the subject should be seen for a final study visit. At this final study visit, the subject will undergo the following evaluations:

- Adverse event assessment (SAEs, SADEs, ADEs that occurred since the last visit)
- Heart failure medication review
- Anticoagulant/antiplatelet medication review
- Reporting of any HF hospitalizations that have occurred since the subject was last seen.

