6.5 IMPLANT VISIT

Following completion of informed consent and collection of the baseline visit, subjects will have a sensor implant. All subjects must have complete implant information provided. The implant procedure will be performed according to the User's Manual/Instructions For Use and the hospital standard of care.

Template: 86357 Rev. A

Page 25 of 65

Clinical Investigational Plan Template

Consented subjects who undergo the implant procedure but without a suitable target pulmonary artery branch will not receive the PA Sensor implant and will be withdrawn from the study after being followed for 30 days for safety (unscheduled visit and withdrawal CRF to be completed). In addition, any subject with a failed PA sensor implant due to any other reasons will be followed for 30 days for safety, then withdrawn from the study, and will resume his/her regular standard of care with his/her physician (unscheduled visit and withdrawal CRF to be completed). If an AE occurred during that period of 30 days, an AE CRF needs to be completed.

If a subject was consented to participate in the study and was implanted but does not meet inclusion/exclusion criteria, this is considered a protocol deviation (PD). A PD form needs to be completed and the sponsor must be informed. The EC and Competent Authority (CA) should be notified (if applicable) about any deviations related to the eligibility criteria.

- The following medical information will be collected at this visit
 - Right Heart Catheterization/implant procedure information
 - o Catheter access information
 - Confirmation of target vessel size
 - Initial PA catheter measurement (PA pressures, Cardiac Output (preferably by measured Modified FICK or thermodilution))
 - Implant location
 - o Device and PA catheter measurements (PA Pressures, Heart Rate, Cardiac Output)
 - Device information
 - Sensor serial number

Prior to hospital discharge, subjects will be trained on the home monitoring system and instructed to take pulmonary artery pressure measurements daily. It is recommended that the pressure measurements be taken at the same time in the morning. Subjects will be supplied with a patient implant identification card, a patient system manual, and a helpline phone number.

It is recommended that subjects who are not being treated with chronic anticoagulant therapy be placed on dual antiplatelet therapy for 1 month following the procedure.

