12.1.1 Freedom from Device/System-related Complications at 12 months

The hypothesis is formulated as:

 H_0 : Freedom from device/system-related complications at 12 months ≤ 0.80

H_a: Freedom from device/system-related complications at 12 months > 0.80

where device/system-related complication is defined in Section 4.4.1.

Sample Size

The CHAMPION Clinical Trial observed 98.6% freedom from device/system-related complications (DSCR) at 12 months⁷. The study size of 230 implanted subjects provides at least 85% power to reject the null hypothesis at the significance level of 5% using exact test for a binomial proportion, under the conservative assumption that freedom from device/system-related complications at 12 months is as low as 87%. The sample size was estimated using PASS 13 (NCSS LLC.).

Subject Group

All subjects who are consented and received a sensor implant or undergo the implant procedure but did not receive a sensor implant regardless of study completion status will be included in the analysis.

Analysis

The desired outcome is to reject the null hypothesis. Subjects not experiencing DSRC prior to withdrawal will be treated as not experiencing a DSRC event. The endpoint will be evaluated using the exact test for a binominal proportion. The null hypothesis will be rejected if the 95% lower confidence bound (LCB) is greater than 0.8.

The freedom from device/system-related complications at 12 months will also be reported using the Kaplan-Meier method.

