12.10 THE EXCLUSION OF PARTICULAR INFORMATION FOR THE TESTING OF THE HYPOTHESIS

No data will be excluded from the analyses to test the study hypotheses.

12.11 IN MULTI-CENTER STUDIES, THE MINIMUM AND MAXIMUM NUMBER OF SUBJECTS TO BE INCLUDED FOR EACH CENTER

This study will attempt to have no more than 15% of subjects at any one center. No minimum number of subjects is required for each center.

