Appendix I. Additional detail regarding sample size calculations

Sample Size for Safety to Demonstrate Superiority to Performance Goal

Freedom from device / system-related complication (CHAMPION reported 0.986)

Numeric Results for testing H0: P = P0 versus H1: P > P0 Test Statistic: Exact Test

	F	Proportion	Performance Goal Proportion				
Power	N	Given H0 (P0)	Given H1 (P1)	Target Alpha	Actual Alpha	Beta	Reject H0 If R ≥ This
0.8631	230	0.8000	0.8700	0.0500	0.0385	0.1369	195
0.8745 0.8850	235 240	0.8000 0.8000	0.8700 0.8700	0.0500 0.0500	0.0402 0.0419	0.1255 0.1150	199 203

Freedom from Sensor Failure (CHAMPION reported 1.00)

Numeric Results for testing H0: P = P0 versus H1: P > P0 Test Statistic: Exact Test

		Proportion	Performance Goal Proportion				
		Given H0	Given H1	Target	Actual		Reject H0
Power	Ν	(P0)	(P1)	Alpha	Alpha	Beta	If R ≥ This
0.8840	230	0.9000	0.9500	0.0500	0.0436	0.1160	215
0.8676	235	0.9000	0.9500	0.0500	0.0350	0.1324	220
0.9043	240	0.9000	0.9500	0.0500	0.0475	0.0957	224

Sample Size Calculations for Heart Failure Hospitalization Rate

The ESC-HF Pilot study showed 29.5% of previously hospitalized patients were rehospitalized for HF by 1 year (see figure below). Since this study included NYHA I and II patients and 24% of the total number of re-hospitalizations were of unknown cause, the actual percent re-hospitalized for NYHA III-only patients is likely to be higher than 29.5%. The CHAMPION study in NYHA III-only patients found that 36.8% of Control patients were rehospitalized for HF by 1 year. Thus the true re-hospitalization rate for European NYHA III patients is likely the same as observed in CHAMPION. Accordingly, the repeat HF hospitalization rate estimates from CHAMPION should serve as good estimates for European patients (Table B). The sample size was calculated using PASS v13.0.10.

Figure A. ESC-HF Pilot Study Results (A.P. Maggioni et al., 2013)

	TREATMENT (270)	CONTROL (280
12 Months	76 (28.2%)	103 (36.8%)

Table B. Sample Size for Effectiveness to Demonstrate Superiority of Treatment to Control Rate

	CHAMPION Treatment Rate at 1	Control Rate at 1 year		Treatment
	Year (Assumes same rate	(Assumes same rate		Sample Size*
Power	in EU Trial)	in EU Registry)	% RRR	(+ 20% W/D)
0.90	0.52	0.75	30.7%	130 (156)
		Registry Rate at 1		
		year		
	EU Treatment Rate at 1 Year	(Assumes worse		
Power	(Assumes worse scenario)	scenario)		Sample Size*
0.90	0.55	0.72	23.6%	234 (281)

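### Section 6.12 lets subjects who carry a permanent sensor be withdrawn for ineligibility or non-compliance, and the primary tests then score them as event-free at 12 months

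*Combined protocol and SAP*

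**What the plan says.** Section 6.12 gives an open-ended list of withdrawal reasons and lets the investigator withdraw a subject at any time with a reasonable rationale. One listed reason is "Subject does not meet the inclusion/exclusion criteria and does not require additional follow-up for safety reasons". Another is non-compliance, with no definition or threshold. Neither mentions implant status.

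Section 6.5 sets a rule for failed implants: 30 days of safety follow-up, then withdrawal. For a consented subject who "was implanted but does not meet inclusion/exclusion criteria, this is considered a protocol deviation (PD"), it requires a form and notification, and says nothing about further follow-up.

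Section 5.3 describes the sensor as permanent. Section 8.2 ends safety surveillance when the subject is withdrawn, unless the protocol specifies otherwise. Section 6.12 asks for a final visit covering adverse events, medication and HF hospitalizations; a pressure reading is not on its list.

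For the complication endpoint, 12.1.1 states: "Subjects not experiencing DSRC prior to withdrawal will be treated as not experiencing a DSRC event". Section 12.1.2 has the same rule for sensor failure. Both analysis sets include subjects regardless of study completion, and both endpoints are also reported by Kaplan-Meier, but the exact binomial test decides. Section 12.10 states: "No data will be excluded from the analyses to test the study hypotheses".

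**The concern.** The 12-month safety question does not end for a subject who still carries the sensor. If the site withdraws that subject for ineligibility or poor compliance, nothing more is observed, yet the subject stays in the denominator as a success. The rule can only move the observed proportion upward.

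The sensor endpoint is the more exposed. Section 4.4.1 defines failure as no obtainable readings after troubleshooting. A subject who stops taking readings may have a failed sensor that nobody has looked for; withdrawn for non-compliance without a reading, that subject is scored as sensor-failure-free.

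Follow-up after exit is also lost for the secondary HF hospitalization comparison (12.1.4) and the compliance summary (12.1.5.2), and subjects withdrawn for poor compliance are unlikely to be typical in either. A different estimator cannot recover events that were never observed; a retention rule prevents the loss.

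**Working it through.** **Inputs.** N = 230 implanted. Goals p0 = 0.80 for complications (the alternative in 12.1.1 is "Freedom from device/system-related complications at 12 months > 0.80") and 0.90 for sensor failure. Success cut-offs of 195 and 215 event-free subjects (Appendix I). The documents give no dropout figure for the safety endpoints, so the number withdrawn, m, and the time of withdrawal are assumptions.

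**Step 1: reproduce the plan.** The Appendix I rows are "0.8631 230 0.8000 0.8700 0.0500 0.0385 0.1369 195" and "0.8840 230 0.9000 0.9500 0.0500 0.0436 0.1160 215". The exact binomial tail gives:
- P(X ≥ 195 | 230, 0.80) = 0.0385; power at 0.87 = 0.8631.
- P(X ≥ 215 | 230, 0.90) = 0.0436; power at 0.95 = 0.8840.

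Both rows reproduce. The one-sided 95% exact lower bound is 0.8034 at 195 and 0.9014 at 215, against 0.7986 and 0.8963 with one success fewer, so the cut-offs match the stated decision rule.

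**Step 2: model the withdrawals.** Take true 12-month freedom equal to the goal and a constant hazard. A subject withdrawn at t months is scored event-free with probability p0^(t/12):
- t = 3: 0.80^0.25 = 0.9457; 0.90^0.25 = 0.9740.
- t = 6: 0.80^0.5 = 0.8944; 0.90^0.5 = 0.9487.

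The number of scored successes is Binomial(m, p0^(t/12)) + Binomial(230 − m, p0). Type I error is the probability that this sum reaches the cut-off.

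| m withdrawn | Time | Complications | Sensor |
|---|---|---|---|
| 0 | – | 3.8% | 4.4% |
| 5 (2%) | 3 months | 4.9% | 5.1% |
| 12 (5%) | 3 months | 6.8% | 6.4% |
| 23 (10%) | 3 months | 10.9% | 8.8% |
| 5 (2%) | 6 months | 4.5% | 4.9% |
| 12 (5%) | 6 months | 5.6% | 5.6% |

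**Step 3: bias in the reported proportion.** For m = 12 at 3 months:
- Complications: (218 × 0.80 + 12 × 0.9457)/230 = 185.75/230 = 0.8076, against a true 0.80.
- Sensor: (218 × 0.90 + 12 × 0.9740)/230 = 207.89/230 = 0.9039, against a true 0.90.

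**Step 4: at the rates the plan cites.** The tests tolerate 230 − 195 = 35 complications and 230 − 215 = 15 sensor failures. At 98.6% freedom about 230 × 0.014 = 3.2 complications are expected, and at 100% no sensor failures. A few unobserved events would hardly change pass/fail.

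**The case against.** The strongest defence is that the ineligibility reason carries its own safeguard: it applies only if no further safety follow-up is needed, and a permanent sensor arguably means that it is. Section 6.12 also asks for all reasonable efforts to retain subjects, for a final visit, and for continued follow-up when an adverse event caused the withdrawal. These points reduce the problem but do not close it. The qualifier is undefined and left to the site, and it does not apply to non-compliance. A general retention sentence does not cancel a listed permission. The final visit need not include a sensor reading.

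It can also be said that the inflation comes from the scoring rule, which applies to every withdrawal reason. That is true. These two reasons are singled out because they are at the investigator's discretion and therefore avoidable.

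Four stronger readings might be inferred, and the documents do not support them:
- That 6.5 keeps implanted ineligible subjects in the study and so contradicts 6.12. It calls the case a deviation and is silent on retention.
- That 12.10 is contradicted. Withdrawn subjects and their collected data stay in; data never collected are not excluded data.
- That non-compliant subjects drop out of the HF hospitalization and usage results. Sections 12.1.3 to 12.1.5 and 12.9 keep them up to exit; only later follow-up is lost.
- That withdrawn subjects are successes without any observation. Events before withdrawal count, including those found at the final visit.

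**Conclusion.** The concern holds as a gap in the withdrawal rules. As written, the plan permits avoidable loss of 12-month safety data in subjects who carry the sensor, and the scoring rule turns that loss into successes.

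The size is conditional. With few and later withdrawals the tests stay below or close to the nominal 5%: 5 subjects at 6 months give 4.5% and 4.9%. With 12 at 3 months they exceed it, at 6.8% and 6.4%. These figures assume true rates exactly at the goals, a constant hazard, and withdrawn subjects with the same risk as the others. If complications cluster around the implant, as the largely procedural list in 3.3 suggests, the complication figures are smaller. If withdrawn subjects carry higher risk, the bias is larger.

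A reader might infer that the study's pass/fail conclusion is in doubt. At the cited 98.6% and 100% it is not; the remaining harm there is some upward bias in the reported 12-month percentages. This is a worthwhile, inexpensive improvement to a study whose primary objective is to demonstrate safety.

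**What to change.** Amend 6.12 as follows, with a matching sentence in 6.5:

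- Limit the ineligibility reason to subjects without a sensor.
- Remove non-compliance as a stand-alone withdrawal reason for implanted subjects.
- State, as a limit on the investigator's general discretion, that an implanted subject found ineligible or non-compliant stays in data collection to month 12 for safety events, sensor status and HF hospitalization, with the deviation recorded, unless the subject withdraws consent. Without this limit, the open-ended list would still allow the same withdrawals.
- Add a sensor-reading check to the final-visit list, so that sensor status is known at exit.

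The change concerns data collection only and leaves the right to withdraw consent intact. It costs amendment wording, the already scheduled 6- and 12-month contacts for a few subjects, and one reading at exit. The reported percentages may be slightly less favourable.

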7.0 COMPLIANCE TO CIP

7.1 STATEMENTS OF COMPLIANCE

The study will be performed in accordance with the most current versions of the World Medical Association (WMA) Declaration of Helsinki, ISO14155 and any regional and/or national regulations.

The investigator will not start enrolling subjects or requesting informed consent from any subject prior to obtaining EC approval and Competent Authority (CA) approval, if applicable, and authorization from the sponsor in writing for the study.

In case additional requirements are imposed by the EC or CA, those requirements will be followed, if appropriate. If any action is taken by an EC and/or CA with respect to the study, that information will be forwarded to St. Jude Medical.

As sponsor, St. Jude Medical has taken up general liability insurance in accordance with the requirements of the applicable local laws.

If required, additional subject coverage or a study specific insurance will be provided by the sponsor as well.

